4. SUBJECT ELIGIBILITY CRITERIA

Each subject must meet all of the following inclusion criteria and none of the exclusion criteria to be enrolled in the study.

4.1. Subject Inclusion Criteria

Phase 1 AND Phase 2:

1. Subject must have a histologically or cytologically confirmed diagnosis of unresectable or metastatic solid tumor malignancy harboring a *KRAS* mutation.
 - Documented *KRAS*^{G12D} mutation as determined by a quantitative polymerase chain reaction (qPCR) or next-generation sequencing (NGS) test performed in a Clinical Laboratory Improvement Amendments (CLIA) laboratory or equivalently accredited diagnostic laboratory. Local tissue-based or liquid biopsy diagnostic testing will be permitted.
 - Adequate tumor tissue needs to be sent to the Sponsor designated central diagnostic laboratory for retrospective confirmation by a central diagnostic laboratory test selected by the Sponsor. See the Study Laboratory Manual for details.
2. Eastern Cooperative Oncology Group (ECOG) Performance Status 0–1
3. Age ≥ 18 (or as required by local regulation).
4. Willing and able to provide written institutional review board (IRB)/ethics committee (EC)-approved Informed Consent.
5. At least 1 measurable target lesion according to Response Evaluation Criteria in Solid Tumors (RECIST) v1.1. Subjects with central nervous system (CNS)-only measurable target lesion ≥ 5 mm as defined by RECIST v1.1 are eligible.
6. Required wash-out time that is related to prior therapies before starting repotrectinib combination treatment:
 - At least 14 days or 5 half-lives (whichever is shorter) must have elapsed after discontinuation of prior systemic therapy and all side effects from prior treatments must have resolved to grade ≤ 1 with the exception of alopecia.
 - At least 14 days must have elapsed after discontinuation of prior immunotherapy and all immune-related side effects from prior immunotherapy must have resolved to grade ≤ 1 .
7. Subjects with asymptomatic CNS metastases (treated or untreated) and/or asymptomatic leptomeningeal carcinomatosis are eligible to enroll if they satisfy the following criteria:
 - Subjects requiring steroids at a stable or decreasing dose (≤ 12 mg/day dexamethasone or equivalent) for at least 14 days.
 - Subjects on stable doses of levetiracetam (same dose for 14 days).
 - A minimum of 14 days must have elapsed from the completion of whole brain radiation treatment (WBRT) before the start of treatment, and all side effects (with the exception of alopecia) from WBRT are resolved to grade ≤ 1 .
 - A minimum of 7 days must have elapsed from the completion of stereotactic radiosurgery before the start of treatment and all side effects (with the exception of alopecia) from stereotactic radiosurgery are resolved to grade ≤ 1 .

8. Baseline laboratory values fulfilling the following requirements:

Absolute Neutrophils Count	$\geq 1,500/\text{mm}^3 (1.5 \times 10^9/\text{L})$
Platelets	$\geq 100,000/\text{mm}^3 (100 \times 10^9/\text{L})$ independent of platelets transfusion support for at least 7 days prior to dosing
Hemoglobin	$\geq 9.0 \text{ g/dL}$ independent of transfusion support for at least 7 days prior to dosing
Creatinine Clearance*	$> 40 \text{ mL/min}$
Total Serum Bilirubin	$< 1.5 \times \text{ULN}$ ($\leq 3.0 \times \text{ULN}$ for patients with Gilbert's Syndrome or liver metastases)
Liver Transaminases (AST/ALT)	$< 2.5 \times \text{ULN}$; $< 5 \times \text{ULN}$ if liver metastases are present
Alkaline Phosphatase	$< 2.5 \times \text{ULN}$; $< 5 \times \text{ULN}$ if liver and/or bone metastasis are present.
Serum Calcium, Magnesium and Potassium	Normal or CTCAE grade ≤ 1 with or without supplementation.

Abbreviations: AST/ALT = aspartate aminotransferase/alanine aminotransferase, ULN = upper limit of normal.

* calculated by Cockcroft and Gault's formula: $(140 - \text{age [yr.]}) \times \text{body weight [kg]} \times 1.23 \times (0.85 \text{ if female}) / \text{serum creatinine } [\mu\text{mol/L}]$.

9. Women of childbearing potential (WOCBP) must have a negative serum pregnancy test during screening and be neither breastfeeding nor intending to become pregnant during study participation. Female patients will be considered to be of childbearing potential unless they have undergone permanent sterilization or are postmenopausal. Postmenopausal is defined as at least 12 months without menses with no other medical reasons (e.g., chemical menopause due to anticancer treatment). For WOCBP and for men, agreement to use a highly effective contraceptive method from the time of screening throughout the study until 4 months (WOCBP) or 6 months (men) after administration of the last dose of any study drug. Highly effective contraceptive methods consist of prior sterilization, intrauterine device (IUD), intrauterine hormone-releasing system (IUS), injectable or implantable contraceptives. All male study subjects must agree to use condoms throughout the study and 6 months after administration of the last dose. Male partners of WOCBP subjects must agree to condom use throughout the study and for 4 months following the last dose of study drug. True abstinence is acceptable if evaluated as consistent with the preferred and the usual lifestyle of the subject. Periodic abstinence is not an acceptable method of contraception.

10. Ability to swallow capsules and tablets intact (without chewing, crushing, or opening).
11. Life expectancy ≥ 3 months.
12. Willingness and ability to comply with scheduled visits, treatment plan, laboratory tests, and other study procedures.

Additional Inclusion Criteria for Phase 1 Only:

13. Subject must have received prior standard therapy appropriate for their tumor type and stage of disease, or in the opinion of the Investigator, would be unlikely to tolerate or derive clinically meaningful benefit from appropriate standard of care therapy.
 - Subject must have received no more than 3 prior systemic regimens.
 - Maintenance therapy will not be counted as a separate regimen.
 - Adjuvant chemotherapy or chemotherapy administered as part of concurrent chemotherapy and radiation therapy will not count as a prior regimen of systemic

therapy as long as recurrence occurred more than 6 months after the last day of chemotherapy.

Additional Inclusion Criteria for Phase 2 Only:

14. Histologically or cytologically confirmed diagnosis of advanced or metastatic NSCLC harboring a *KRAS*^{G12D} mutation.
 - Subject must have a documented *KRAS*^{G12D} mutation as determined by a qPCR or NGS test performed in a CLIA laboratory or equivalently accredited diagnostic laboratory. Local tissue-based or liquid biopsy diagnostic testing will be permitted.
 - Adequate tumor tissue needs to be sent to the Sponsor designated central diagnostic laboratory for retrospective confirmation by a central diagnostic laboratory test selected by the Sponsor. See the Study Laboratory Manual for details.
15. Subjects must have received no more than one prior line of platinum-based chemotherapy **OR** one prior line of platinum-based chemotherapy in combination with immunotherapy **OR** both platinum-based chemotherapy and single agent anti-PD1/PDL1 therapy in two separate lines of therapy.
 - Adjuvant chemotherapy or chemotherapy administered as part of concurrent chemotherapy and radiation therapy for the treatment of lung cancer will not count as a prior regimen of systemic therapy as long as recurrence of patient's lung cancer occurred more than 12 months after the last day of chemotherapy.

4.2. Subject Exclusion Criteria

1. Concurrent participation in another therapeutic clinical trial.
2. Symptomatic brain metastases or leptomeningeal involvement.
3. History of previous cancer requiring therapy within the previous 2 years, except for squamous cell or basal-cell carcinoma of the skin, or any in situ carcinoma that has been completely resected.
4. Major surgery within 4 weeks of start of treatment. Radiation therapy (except palliative to relieve bone pain) within 2 weeks of start of treatment. Palliative radiation (≤ 10 fractions) must have been completed at least 48 hours prior to start of treatment.
5. Clinically significant cardiovascular disease (either active or within 6 months prior to start of treatment): myocardial infarction, unstable angina, coronary/peripheral artery bypass graft, symptomatic congestive heart failure (New York Heart Association Classification Class $\geq II$), cerebrovascular accident or transient ischemic attack, symptomatic bradycardia, requirement for anti-arrhythmic medication. Ongoing cardiac dysrhythmias of CTCAE grade ≥ 2 .
6. Any of the following cardiac criteria:
 - Mean resting corrected QT interval (ECG interval measured from the onset of the QRS complex to the end of the T wave) for heart rate (QTc) > 470 msec obtained from 3 ECGs, using the screening clinic ECG machine-derived QTc value
 - Any clinically important abnormalities in rhythm, conduction or morphology of resting ECG (e.g., complete left bundle branch block, third degree heart block, second degree heart block, PR interval > 250 msec)

- Any factors that increase the risk of QTc prolongation or risk of arrhythmic events such as heart failure, hypokalemia, congenital long QT syndrome, family history of long QT syndrome, or any concomitant medication known to prolong the QT interval

7. Known clinically significant active infections not controlled with systemic treatment (bacterial, fungal, viral including human immunodeficiency virus [HIV] positivity, hepatitis B [HBV], and hepatitis C [HCV], and acquired immunodeficiency syndrome [AIDS]-related illness).

8. Gastrointestinal disease (e.g., Crohn's disease, ulcerative colitis, or short gut syndrome) or other malabsorption syndromes that would impact drug absorption.

9. Peripheral neuropathy, paresthesia, dizziness, dysgeusia, muscle weakness, ataxia grade ≥ 2 .

10. Currently have or had a history of ILD, radiation pneumonitis that required steroid treatment, or drug-related pneumonitis.

11. Other severe acute or chronic medical or psychiatric condition or laboratory abnormality that may increase the risk associated with study participation or study drug administration, or that may interfere with the interpretation of study results and, in the judgment of the Investigator and/or Turning Point Therapeutics, would make the subject inappropriate for entry into this study, or could compromise protocol objectives in the opinion of the Investigator and/or Turning Point Therapeutics.

12. Current or anticipated use of drugs that are known to be strong CYP3A inhibitors or inducers as well as use of drugs that are sensitive CYP3A substrates as listed in [Appendix 1](#).

13. Prior exposure to repotrectinib.

14. Prior exposure to a direct and specific inhibitor of KRAS.

15. Prior exposure to trametinib or another MEK inhibitor.

16. Subjects have a history or current evidence of retinal vein occlusion (RVO) or central serous retinopathy (CSR) determined by an ophthalmology exam.

17. Current or anticipated use of drugs that are sensitive substrate with narrow therapeutic index for UGT1A1.

18. Current or anticipated use of drugs that are sensitive substrate with narrow therapeutic index for OATP1B1, OAT3, MATE1, and MATE2-K.

19. Current or anticipated use of drugs that are strong inhibitors of P-glycoprotein.

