5.4. Concomitant Treatments

Any concomitant medications, blood products, as well as non-drug supportive interventions (e.g., paracentesis) received by subjects from the date of signed informed consent until the EOT visit should be recorded on the appropriate electronic Case Report Form (eCRF). The Investigator should be alerted if the subject is taking any agent known to affect or with the potential for drug interactions.

Note on COVID-19 Vaccination: The use of vaccines is not a restriction for this study. Currently enrolled and potential adult clinical trial subjects are allowed to receive the COVID-19 vaccine with no impact on their eligibility or ability to remain on study treatment. This guidance will also apply to pediatric and adolescent patients once vaccine approval is available for these populations. In addition, there is not a required wash-out period for the vaccine. The risk-benefit for COVID-19 vaccination while on study should be determined by the treating physician. Administration of the COVID-19 vaccine will be recorded in the medical history or the concomitant medications CRF, as applicable, as well as any adverse events related to the vaccine.

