5.4.1. Prohibited Concomitant Medications

The concomitant use of known strong CYP3A4 inhibitors is prohibited including their administration at least within 2 weeks prior to the first study drug dose and throughout the study.

Subjects should avoid grapefruit juice or grapefruit/grapefruit-related citrus fruits (Seville oranges, pomelos). Coadministration of study drug in combination with strong CYP3A4 inducers is prohibited including their administration at least within 2 weeks prior to the first study drug dose and throughout the study. See [Appendix 1](#) for a list of known CYP3A4 inhibitors and inducers.

Current or anticipated use of drugs that are sensitive CYP3A4 substrates should be avoided including their administration at least within 2 weeks prior to the first study drug dose and throughout the study. Concomitant medication suspected of being a sensitive CYP3A4 substrate must be approved by the Sponsor.

Current or anticipated use of drugs that are sensitive substrate with narrow therapeutic index for UGT1A1 should be avoided, including their administration within at least 2 weeks prior to the first study drug dose and throughout the study. Concomitant medication suspected of being a sensitive UGT1A1 substrate with narrow therapeutic index must be approved by the Sponsor.

Concomitant use of drugs that are known to be sensitive substrates with narrow therapeutic index for OATP1B1, OAT3, MATE1, and MATE2-K should be avoided including their administration at least within 2 weeks prior to the first study drug dose and throughout the study. Concomitant medication suspected of being a sensitive OATP1B1, OAT3, MATE1 and MATE2-K substrate with narrow therapeutic index must be approved by the Sponsor.

Current or anticipated use of drugs that are strong inhibitors of P-gp should be avoided, including their administration within at least 2 weeks prior to the first study drug dose and throughout the study. Concomitant medication with suspected strong P-gp inhibitory effect must be approved by the Sponsor.

If there is a question about a particular concomitant medication, discuss with the Medical Monitor.

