7.8. Restrictions

7.8.1. Concomitant Medications

Please refer to [Section 5.4.1](#) for Prohibited Concomitant Medications.

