SENSITIVE CYP3A SUBSTRATES AND MEDICATIONS
THAT CAUSE QTC PROLONGATION**

Strong CYP3A Inhibitors or Inducers

Strong CYP3A Inhibitors	Strong CYP3A Inducers
Macrolide antibiotics: clarithromycin and telithromycin	Carbamazepine
	Efavirenz
Anti-fungal: itraconazole, ketoconazole, voriconazole, posaconazole	Phenobarbital
	Phenytoin
Anti-virals: lopinavir, indinavir, nelfinavir, ritonavir, saquinavir, amprenavir	Rifampin
	Rifabutin
Conivaptan	Rifapentine
Mibepradil	St John's wort
Nefazodone	
Troleandomycin	
Miscellaneous: Grapefruit juice	

Sensitive CYP3A Substrates

alfentanil	avanafil	buspirone	conivaptan
darifenacin	darunavir	ebastine	everolimus
ibrutinib	lomitapide	lovastatin	midazolam
naloxegol	nisoldipine	saquinavir	simvastatin
sirolimus	tacrolimus	tipranavir	triazolam
vardenafil	budesonide	dasatinib	dronedarone
eletriptan	eplerenone	felodipine	indinavir
lurasidone	maraviroc	quetiapine	sildenafil
ticagrelor	tolvaptan		

Medications That Cause QTc Prolongation

Amiodarone	Astemizole	Azithromycin	Chlorpromazine
Disopyramide	Terfenadine	Clarithromycin	Haloperidol
Dofetilide	Chloroquine	Erythromycin	Mesoridazine
Flecainide	Halofantrine	Moxifloxacin	Pimozide
Ibutilide	Probuconol	Sparfloxacin	Thioridazine
Procainamide	Pentamidine	Domperidone	Levomethadyl
Quinidine	Bepridil	Droperidol	Methadone
Sotalol	Arsenic trioxide	Vandetanib	Citalopram
Cisapride			

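### QT-prolonging drugs bar entry under exclusion 6, but no on-study rule restricts them as a class, so most drugs on the Appendix 1 QTc list may be started during treatment

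*Combined protocol and SAP*

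**What the plan says.** The third bullet of exclusion 6 (Section 4.2 and synopsis) lists "any concomitant medication known to prolong the QT interval" among the factors that exclude a subject. It cites no drug list and does not mention anticipated use. Exclusions 12, 17, 18 and 19 do look ahead; exclusion 19, for example, reads "Current or anticipated use of drugs that are strong inhibitors of P-glycoprotein".

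Section 5.4.1 sets the on-study restrictions. It covers strong CYP3A4 inhibitors, strong CYP3A4 inducers, sensitive CYP3A4 substrates, and strong P-gp inhibitors. It also covers narrow-index substrates of UGT1A1 and of four named transporters. It refers to Appendix 1 "for a list of known CYP3A4 inhibitors and inducers". For P-gp it adds an approval step: "Concomitant medication with suspected strong P-gp inhibitory effect must be approved by the Sponsor". Section 7.8.1 refers the reader to 5.4.1 "for Prohibited Concomitant Medications" and adds nothing of its own.

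The title of Appendix 1 includes "MEDICATIONS THAT CAUSE QTC PROLONGATION", and the appendix contains a table of such drugs.

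**The concern.** The plan regards a QT-prolonging co-medication as enough of a hazard to refuse entry. Section 6.13.1 also names such drugs among the reversible causes to correct once a QTc above 500 msec has been verified. Yet a subject who enters free of these drugs can be given one the following week without breaching 5.4.1, provided the drug falls in no other restricted class.

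What is at stake is patient safety. The decision to avoid the drug rests on the prescriber noticing a possible problem or choosing to ask, although the sponsor has already written the list that could inform a rule. The sample size, the error rates and the efficacy analysis are not affected.

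**Working it through.** The plan gives no figure to reproduce. The check compares the rules and counts list entries.

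**1. Reach of the entry rule.** The opening sentence of Section 4 makes the inclusion and exclusion criteria conditions for being enrolled. Exclusion 6 therefore does not govern drugs started later.

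**2. Entry rules against on-study rules.**

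| Entry rule (4.2) | Looks ahead to anticipated use? | Restrictions in 5.4.1 running throughout the study |
|---|---|---|
| 12: CYP3A inhibitors, inducers, sensitive substrates | Yes | 3 |
| 17: UGT1A1 substrates | Yes | 1 |
| 18: OATP1B1, OAT3, MATE1, MATE2-K substrates | Yes | 1 |
| 19: strong P-gp inhibitors | Yes | 1 |
| 6: QT-prolonging drugs | No | 0 |

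The total in 5.4.1 is 3 + 1 + 1 + 1 = 6 restrictions, with no QT class among them.

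**3. Use of Appendix 1.** Two rules cite it, exclusion 12 and 5.4.1, both for CYP3A drugs. No rule cites its QTc list.

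**4. Size of the list and overlap.** The QTc table has 8 full rows of 4 and one further entry: 8 × 4 + 1 = 33. Compared by hand with the Appendix 1 CYP3A inhibitor, inducer and substrate lists, one drug appears in both: clarithromycin, a strong CYP3A inhibitor. That leaves 33 − 1 = 32 entries on no CYP3A list, among them azithromycin, moxifloxacin, citalopram, haloperidol and domperidone.

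The 32 is an upper bound on the drugs left open. Section 5.4.1.1 bars additional systemic anti-tumor therapy, so any anti-tumor agent on the list is closed off by that route. The UGT1A1, transporter and P-gp restrictions come without drug lists, so further entries may be caught there; the documents do not say which.

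**5. What the other safeguards do before such a drug is started.**

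- *Medication review.* The Schedule of Activities marks it at each visit from Screening to Safety Follow-up, and Section 7.2.1 lists it among the pre-dose assessments. It records what has been taken and sets no QT rule.
- *Section 5.4 alert.* "The Investigator should be alerted if the subject is taking any agent known to affect or with the potential for drug interactions". This informs the Investigator and neither prohibits a drug nor requires approval.
- *Medical Monitor.* Section 5.4.1 advises discussion "If there is a question about a particular concomitant medication". It applies only if somebody raises the question.
- *Sections 5.4.2 and 5.4.3.* Both require that no interaction be known or expected, and 5.4.2 adds Sponsor approval. They cover only prophylaxis of diarrhea, nausea and vomiting (5.4.2) and anti-inflammatory or narcotic analgesic drugs (5.4.3). Their cross-check is against Section 5.4 or its prohibited list, which has no QT class.
- *ECG monitoring, Table 4 and Section 6.13.1.* These act once QTc is measured. Table 4 calls for review of co-medications from Grade 1, with dosing continued at Grades 1 and 2. Section 6.13.1 holds drug above 500 msec and removes the subject above 515 msec.

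The first and last of these detect a drug or its effect after it has been started. The others depend on someone noticing or asking, or apply only to particular drug types.

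**The case against.** The best defence is that the plan chose monitoring over prohibition. The classes in 5.4.1 concern metabolism and transport, whereas QT risk has its own cardiac section (6.13) and its own row in Table 4. Entry rules may properly be stricter than on-study rules: the same bullet of exclusion 6 names hypokalemia, which is managed rather than prohibited once treatment begins. The comparison of four carried-over exclusions with one that was not is also selective, because those four are all interaction classes. The safeguards are real. Section 1.4.1 reports minimal effects of repotrectinib on human ion channels (hERG IC50 18 μM), and exclusion 5 makes later need for the listed anti-arrhythmics less likely.

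Much of this stands as a limit on the size of the point. It does not explain why the sponsor compiled a QTc drug list and attached no rule to it, or why a drug that bars entry needs no approval afterwards. Hypokalemia is a poor parallel: it can arise unbidden, whereas starting a drug is a decision that a rule can govern.

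Some readers might infer that every listed drug is freely permitted. The documents do not support that, given clarithromycin, 5.4.1.1 and the classes without lists. Others might infer that nothing on study would bring such a drug to light; medication review at each visit contradicts that. The spacing of scheduled ECGs might also seem to strengthen the case, but it has no bearing on whether a QT-prolonging drug may be started.

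**Conclusion.** The gap is real and limited. The plan bars QT-prolonging co-medication at enrolment, has no on-study QT class, and leaves its own 33-entry QTc list uncited. At most 32 of those entries may be started on treatment without breaching the CYP3A restrictions that rely on Appendix 1. The number left open after every other rule is applied cannot be fixed from the documents, but it includes most of the list unless the classes without lists prove very broad.

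These counts describe how the rules fit together and do not measure risk. A reader might infer that the combination is known to prolong QT, or that harm is likely. The documents report no QT signal and give no rate of QTc events or of use of these drugs, so neither inference is supported. The conclusion rests on reading exclusion 6 as an entry condition, as Section 4 states, and on 5.4.1 and 5.4.1.1 being the operative prohibited lists. It is worth correcting as a cheap patient-safety alignment.

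**What to change.** 1. Add to Section 5.4.1 that drugs known to prolong the QT interval, including those on the Appendix 1 QTc list (non-exhaustive), should be avoided throughout the study unless approved by the Sponsor. The approval wording already used for P-gp inhibitors can serve as the model.
2. In exclusion 6, in both Section 4.2 and the synopsis, cover anticipated as well as current use, and cite the Appendix 1 QTc list.

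Sections 7.8.1 and 5.4.2 already refer to the prohibited list, so the new class would reach them without further change. Section 5.4.3 refers to Section 5.4 generally and could cite 5.4.1 for clarity.

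The edit is wording only, since the list and the approval language exist. In operation it means more queries to the Medical Monitor and possible short delays to some supportive-care drugs, which Section 7.8.4 otherwise leaves to the Investigator. Sponsor approval keeps a necessary drug available.
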